8.1.3 Safety Variables

Adverse events (AEs), all AEs, AEs Grade 3 or 4, AEs leading to treatment interruption and discontinuation, serious adverse events (SAEs), premature discontinuation from study and treatment, laboratory parameters, exposure to study medication and skin evaluation, head/neck evaluations, chest CT scan will be the primary safety variables for each cohort. Vital signs, electrocardiogram, ECOG performance status, and physical examination will be the secondary safety variables.

For Cohort 3b, patients with colorectal cancer, dose-limiting toxicities parameters as defined in [Section 6.3.2.2](#) will be summarized by dose levels.

8.2 STUDY POPULATIONS

The main analysis population for the efficacy analysis will be the intent-to-treat (ITT) population, which will include all patients enrolled in the study irrespective of whether they have received study medication or not. ITT1 to ITT7 will correspond to the ITT population for each cohort (Cohort 1 to Cohort 7, respectively).

The per-protocol (PP) population will not be defined due to the small number of patients per cohort, but protocol deviations will be listed (including patients with non-measurable disease at baseline).

The safety populations SP1 to SP7 will correspond to the safety populations for Cohort 1 to Cohort 7, respectively, and will include, for each cohort, all patients who have received at least one dose of study medication.

Cohort 7 (patients with other solid tumours) will include patients with different tumour types and therefore different safety/ITT populations will be defined for different tumour types.

8.3 STATISTICAL AND ANALYTICAL METHODS

8.3.1 Statistical Model

The main analysis for RR will use an adaptive design based on Simon's two stage design for a single proportion (70).

Stage I will be defined as when a pre-specified number of patients (as determined in the Sample Size section) will have a minimum of 8 weeks of treatment, develop progressive disease, prematurely withdraw from the study medication, or die, whichever occurs first.

If a pre-specified minimal RR will not be achieved in certain cohorts in the first stage of the study in certain cohorts, this cohort will be closed and no further enrolment of patients will be performed for that cohort. However, if a clear clinical benefit has been observed for patients in the cohort, e.g. majority of patients recorded SD at Week 8 and no CR or PR is recorded, then enrolment into Stage II might be allowed for this cohort after discussion with the Sponsor and study Steering Committee. Otherwise, enrolment will continue into Stage II until a pre-determined number of additional patients has been reached (as explained in the Sample Size section). At the conclusion of this study, vemurafenib will be declared effective or ineffective for each indication (cohort) based on rules for Stage II.

The analysis at Stage II (for lower or higher desirable response) for each cohort will be performed when all patients enrolled in the study, as estimated in the Sample Size section, will have a minimum of 8 weeks of treatment, develop progressive disease, withdraw, or are lost to follow-up, whichever occurs first.

Recruitment into any cohort/indication can be expanded up to a total of 70 patients if a response rate has been demonstrated in Stage II of that cohort as per stopping rules defined in the protocol or a clear clinical benefit for patients is observed. This will be decided by the Sponsor in discussion with study Steering Committee.

In case a cohort/indication is expanded to up to 70 patients, the primary analysis for efficacy will occur once all patients have been followed up for 9 months after last patient had been enrolled in that cohort, or the patient develops progressive disease, withdraws consent, or is lost to follow-up, whichever occurs first.

The final analysis for each cohort will take place when all patients in that cohort have been followed for survival for a minimum of 12 months after the last patient has been enrolled or until all patients have died withdrawn consent or are lost to follow up, whichever occurs first. More details are provided in Efficacy Data Analysis (see below).

8.3.1.1 Hypothesis Testing

The adaptive two-stage design allows the original estimation of the Stage II RR to be reassessed, based on information at Stage I, in the event that it was too optimistic or too sceptical to be the true RR.

For example, for patients in each cohort, we assume that an RR of 15% would be a very low RR and vemurafenib would be "under-performing" for this cohort. An RR of 45% would be a high desirable RR, whereas an RR of 35% would be a low desirable RR, for Stage II.

The hypotheses for all cohorts for Stage I are:

$$H_0: \pi_{N1} < \pi_0 \text{ where } \pi_0 = 15\%$$

$$H_1: \pi_{N1} \geq \pi_0 \text{ where } \pi_0 = 15\%$$

If H_0 is rejected (and H_1 is accepted at Stage I), further patients will be enrolled based on the number of responders in Stage I and their data will be collected in the second stage.

The hypotheses for all cohorts at the end of Stage II for a low desirable response, π_{1L} , are:

- i) H_1 is accepted at Stage I and
- ii) $H_0: \pi_N \leq \pi_{1L}$ where $\pi_{1L} = 35\%$

$$H_1: \pi_N > \pi_{1L} \text{ where } \pi_{1L} = 35\%$$

The N notifies the total number of patients for each cohort.

The hypotheses for all cohorts at the end of Stage II for a high desirable response, π_{1H} , are:

- i) H_1 is accepted at Stage I and
- ii) $H_0: \pi_N \leq \pi_{1H}$ where $\pi_{1H} = 45\%$

$$H_1: \pi_N > \pi_{1H} \text{ where } \pi_{1H} = 45\%$$

Cohort 3b

For this cohort, first, the recommended dose for Stage I/II part should be established based on 3+3 classical design. Then the second part will include a stage I and II parts similar to what is planned for the other cohorts and same statistical hypotheses at Stage I and Stage II will be applied.

8.3.1.2 Stopping Rules for Enrolment and Screening

If no patients are enrolled in the remaining cohorts one year after any of the cohorts has completed enrolment, then enrolment in those remaining cohorts will be stopped (patients already in screening will be allowed to enrol if eligible).

Individual cohorts may temporarily stop enrolment to allow for the stage I analysis before progressing to stage II.

Individual cohorts may temporarily stop screening to allow for the stage I analysis before progressing to stage II.

The decision to carry on enrolment of CRC patients into Cohort 3a (vemurafenib monotherapy) and/or enrol patients into Cohort 3b (combination of vemurafenib and cetuximab) will be based on the stage I analysis for Cohort 3a (vemurafenib monotherapy). This will be decided by the Sponsor in discussion with study Steering Committee.

The decision to continue enrolment in Cohort 3b after the Part I dose escalation phase will be decided by the Sponsor in discussion with study Steering Committee.

1. Rules for Stage I

Stage I will be stopped if the number of responders (unconfirmed) is less than the pre-specified number in the [Table 15](#) (e.g. if there is none or only one responder out of first seven patients). However if a clear clinical benefit has been observed for patients in the cohort, e.g. majority of patients recorded SD at Week 8 and no CR or PR is recorded, then enrolment into Stage II might be allowed for this cohort.

If there is the required response during Stage I or a good clinical benefit is observed for particular cohort as mentioned above, then additional patients will be enrolled in the second stage of the corresponding cohort, in order to achieve total number of patients as specified in the [Table 15](#) and [Table 16](#) below (Sample Size estimation section).

Cohort 7 will be closed to enrolment when all other cohorts are closed and results are reported, regardless of the number of patients recruited at that time. This cohort may be quite heterogeneous and will be examined primarily to seek efficacy signals in the relatively rare BRAF V600 mutation-positive tumours.

2. Rules for Stage II

A study treatment will be considered to be efficacious in a cohort in Stage II if

- there is no unacceptable toxicity and
- the number of responders is equal or above the specified number in the sample size calculations, as presented in [Table 16](#) or
- best overall response, BOR (confirmed) is higher than 15%.

3. Cohort Expansion

There will be no formal statistical hypothesis tested as part of the expansion cohort analysis. The analysis of the expanded cohort will allow estimation of RR and other efficacy parameters (please refer to secondary efficacy parameters in [Section 8.1.2](#)) with increased precision and more insight concerning the safety profile.

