However, if the number of responders is 2, 3, or 4 out of 7 patients in Stage I, then the study medication is possibly efficacious for that cohort and further data at stage II will be collected based on the "low desirable response at Stage II" Sample Size estimation, i.e., an additional 12 patients will be enrolled in order to have a total of 19 patients for that cohort. Stage I will be stopped if the number of responders is less than the pre-specified number in the [Table 15](#) (e.g. if there is none or only one responder out of first seven patients). However if a clear clinical benefit has been observed for patients in the cohort, e.g. majority of patients recorded SD at Week 8 and no CR or PR is recorded, then enrolment into Stage II will be allowed for this cohort after discussion with the Sponsor and study Steering Committee.

If there are 5 or more responders out of 7, then further data will be collected based on "high desirable response at Stage II" Sample Size estimation, i.e., an additional 6 patients will be enrolled in order to have a total of 13 patients for that cohort.

Assuming RRs as specified in the prior hypothesis testing, a power of 80% for high desirable response and 70% for low desirable response and two-sided alpha of 0.1, the number of patients required in each cohort is presented in [Table 16](#).

Table 15:
Sample Size for Each Cohort – Stage I/II

	Dose Finding ^a	Sample size following Stage I analysis	
		Low desirable response	High desirable response
NSCLC		19	13
Ovarian cancer		19	13
Colorectal cancer (Cohort 3a vemurafenib only)		19	13
Colorectal cancer (Cohort 3b vemurafenib and cetuximab)	3+3 Design up to 18	19	13
Cholangiocarcinoma/cancer of biliary tract		19	13
Breast Cancer		19	13
Multiple Myeloma		19	13
Other tumours ^b		19	13
Total number for Stage I/II	up to 170 patients ^c		

- a. Cohort 3b Part 1 only
- b. The n's presented are for each individual tumour type, with enough patients available to follow the 2 stage study design
- c. The total number of patients may exceed the original estimate of 170 patients if any cohort is expanded (see [Table 16](#)).

Details regarding Stage I and number of responders are presented in [Table 16](#).

Table 16:
Sample Size for Each Cohort (except Cohort 6) and Stage I/II

	Stage (Two-Stage Design)		Total Number of Patients in Each Cohort	Two-Sided Alpha Level / Power
	Stage I	Stage II ^b		
All Cohorts				
Low response at the end of Stage I				

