Number of patients	7	19	19	10% / 70%
Number of responders ^a	≥ 2 and ≤ 4	≥ 5		
High response at the end of Stage I				
Number of patients	7	13	13	10% / 80%
Number of responders ^a	≥ 5	≥ 6		

The sample size was estimated using the method of Lin and Shih's paper (Biometrics. 2004;60:482-490) and corresponding SAS program.

Number of patients needed to respond in order to continue into Stage II or have a positive result at the end of trial.

- a. This columns display a maximum number of patients required for each cohort and number of responders that should be present at end of Stage II in order to declare efficacious treatment.

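### The Stage II success rule accepts a confirmed BOR just above 15%, the plan's own undesirable rate, so 3 of 19 is enough and the false-positive rate rises from 10% to about 18–25%

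*Protocol*

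**What the plan says.** - **Undesirable rate.** Section 8.3.1.1: "we assume that an RR of 15% would be a very low RR". The targets follow: "An RR of 45% would be a high desirable RR, whereas an RR of 35% would be a low desirable RR, for Stage II".
- **Error rates.** Section 8.4 sizes each cohort for "a power of 80% for high desirable response and 70% for low desirable response and two-sided alpha of 0.1".
- **Stage I.** A cohort stops, for example, "if there is none or only one responder out of first seven patients". With 2 to 4 responders of 7, "an additional 12 patients will be enrolled in order to have a total of 19 patients for that cohort"; with 5 or more, "an additional 6 patients will be enrolled in order to have a total of 13 patients for that cohort".
- **Stage II count.** Table 16 requires at least 5 of 19 or at least 6 of 13. Its footnote describes this as the "number of responders that should be present at end of Stage II in order to declare efficacious treatment".
- **Stage II rule.** Section 8.3.1.2, repeated in the synopsis, lists three bullets: no unacceptable toxicity, *and* the Table 16 count reached, *or* "best overall response, BOR (confirmed) is higher than 15" per cent.
- **Consequence.** Section 8.3.1 says the drug will be declared effective or ineffective in each cohort by the Stage II rules. It also makes a demonstrated Stage II response one of the grounds for expanding a cohort to 70 patients.

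**The concern.** The third bullet compares a bare point estimate with the rate the plan itself regards as too low. It has no confidence bound and no share of alpha. Because it is an alternative to the Table 16 count, it can only add ways to succeed, so the 10% in Table 16 cannot describe the rule actually written. It also contradicts the Table 16 footnote, which makes the count a requirement for declaring efficacy.

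At stake is the trial's main decision. A cohort responding at the under-performing rate could be declared effective, and that declaration is a stated ground for expansion. Section 8.3.1.2 says no formal hypothesis is tested in the expansion, so nothing later formally corrects a false positive.

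The and/or list is also unbracketed. Read as (no unacceptable toxicity and count) or BOR, the BOR route bypasses the toxicity condition.

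**Working it through.** **Inputs.** Undesirable rate 15% and low desirable rate 35% (section 8.3.1.1). Stage I n = 7, continue at 2 or more; totals 19 or 13; thresholds 5 and 6 (section 8.4, Table 16). BOR cut 15% (section 8.3.1.2). The protocol gives no confirmation share for this trial. Its melanoma data give 56.3/81.3 = 0.69 (section 1.3.4.1) and 57/69 = 0.83 (section 1.3.4.2).

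**Step 1: what the BOR cut means in counts.** 2/19 = 10.5% fails and 3/19 = 15.8% passes. In the 13-patient arm 2/13 = 15.4% passes, but that arm is reached with probability only 0.12% at a true 15%, so it hardly matters. The exact 95% interval for 3/19 is about 3% to 40%.

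**Step 2: reproduce the plan's figures.** With x the Stage I responders and p the true rate,

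P(success) = Σ(x = 2..4) b(x; 7, p) · P[Bin(12, p) ≥ 5 − x] + Σ(x = 5..7) b(x; 7, p) · P[Bin(6, p) ≥ 6 − x].

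For the BOR route with every response confirmed, replace 5 by 3 and 6 by 2. At p = 0.15:

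| x of 7 | P(x) | P(reach Table 16 count) | P(reach 3/19 or 2/13) | Product, Table 16 | Product, BOR route |
|---|---|---|---|---|---|
| 2 | 0.2097 | 0.2642 | 0.8578 | 0.0554 | 0.1798 |
| 3 | 0.0617 | 0.5565 | 1 | 0.0343 | 0.0617 |
| 4 | 0.0109 | 0.8578 | 1 | 0.0093 | 0.0109 |
| 5–7 | 0.0012 | – | 1 | 0.0008 | 0.0012 |
| Sum | 0.2834 | | | **0.0998** | **0.2536** |

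Table 16 alone gives 0.0998 against the stated 10%. At p = 0.35 the same formula gives 0.705 against the stated 70%. At p = 0.45 it gives 0.883, so the stated 80% is met as a minimum. The stated alpha and power therefore belong to the count rule alone. The 10% is a one-sided exact error, although labelled two-sided.

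**Step 3: effect of the 'or'.** After 2 confirmed responders in Stage I, one more in 12 is enough: 1 − 0.85^12 = 0.858. Of cohorts that pass Stage I at a true 15%, 0.254/0.283, about nine in ten, are then declared efficacious.

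**Step 4: allow for unconfirmed responses.** Each Week 8 response is confirmed with share c. Success is a Week 8 count at the Table 16 threshold, or confirmed responses/n > 0.15. At a true Week 8 rate of 15%:

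| Confirmation share c | No later responders | Later responders keep confirmed BOR at 15% |
|---|---|---|
| 1.00 | 25.4% | 25.4% |
| 0.83 | 21.1% | 23.4% |
| 0.69 | 17.6% | 22.4% |
| 0.50 | 13.5% | 21.4% |

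With c = 1 and a further 5% responding late, the figure is 27.3%.

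**Step 5: what the clause buys.** At p = 0.35 success rises from 0.705 to at most 0.765 (c = 1).

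**Step 6: across the trial.** If all eight rows of Table 15 were truly at 15%, expected false positives would be 8 × 0.0998 = 0.8 under Table 16 and 8 × 0.254 = 2.0 with the BOR route at c = 1.

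**The case against.** The arithmetic is not in dispute. The case on the other side concerns size and weight.

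- **Confirmation share.** The 18–25% range rests on melanoma shares or on full confirmation, and section 1.3.4 makes reproducibility in other tumours a question for this study. At a share of 0.5 with no late responders the rate is 13.5%, and at 0.4 it is 11.9%. This stands as a limit on the number. Late responses, which BOR counts, push the other way.
- **Timing.** Section 8.3.1 triggers the Stage II analysis after a minimum of 8 weeks of treatment, but solid-tumour scans are 8 weeks apart and confirmation needs at least 4 weeks. At the earliest cut, the last-enrolled responders could not yet be confirmed. If that affects the last 3 of the 12 Stage II patients, the figures become 23.5%, 19.1% and 16.0% at shares 1.0, 0.83 and 0.69; with 6 of 12 they are 20.8%, 16.8% and 14.4%. All remain above 10%, and a later BOR reading removes the effect.
- **Different endpoints.** The 15% is set for Week 8 RR, not for confirmed BOR. That is true, but the protocol states no separate undesirable rate for BOR, and the added route raises the error whatever that rate is.
- **Expansion.** It is decided by the sponsor with the Steering Committee and may also rest on clear clinical benefit. So the clause neither forces expansion nor is the only way to it. This stands.
- **Expected count.** Two false positives is a worst case. With seven rows at 17.6% it is 7 × 0.176 = 1.2, against 7 × 0.0998 = 0.7. This stands too.
- **Exploratory phase II.** A lenient go rule can be deliberate. But section 8.3.2 waives adjustment across cohorts, not the 10% stated within each cohort, and the protocol speaks of declaring the drug effective.
- **Toxicity bypass.** This is one reading of an ambiguous list, so it is a drafting point.

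**Conclusion.** The concern holds. The 10% alpha in Table 16 is true of the count rule and not of the decision rule in section 8.3.1.2. With the BOR route, the chance of declaring a cohort effective at a true 15% is about 18–25% for confirmation shares of 0.69 to 1.0, assuming the Stage I gate is kept, BOR is read late enough for confirmation, and no responses occur after Week 8. Lower shares or an early cut bring it nearer to 10%. Late responders raise it, as does continuing past Stage I on clinical benefit: if every 0-of-7 cohort continued, the all-confirmed figure would be 33.8%. Every scenario examined stays above 10%, and nothing else in the protocol controls the error. The gain at a true 35% is at most 6 percentage points.

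**What to change.** Delete the BOR bullet from the Stage II rules in section 8.3.1.2 and in the synopsis, so that the rule reads: no unacceptable toxicity and responders at or above the Table 16 number. This also removes the bracketing ambiguity and agrees with the Table 16 footnote. Confirmed BOR can still be reported with its Clopper-Pearson interval, set beside the same counts (5 of 19, 6 of 13), as a supportive result and not as an alternative route to success.

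The cost is one sentence in two places and no patients. The chance of a positive call at a true 35% goes back from at most 76.5% to 70.5%, which is the 70% the plan states. If the sponsor prefers the looser rule, section 8.4 should give its actual error rate, the assumed confirmation share, the time at which BOR is read, and brackets showing how far the toxicity condition reaches.

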8.3.2 Efficacy Data Analysis

The primary efficacy endpoint is RR at Week 8 in each cohort, as assessed by the Investigator using RECIST, v1.1 or IMWG response criteria.

This is an early phase II study and cohorts are independent, hence there will be no adjustment for multiplicity.

Number and percentage of responders with corresponding Clopper-Pearson 95% confidence intervals will be provided for each cohort. The clinical benefit rate, BOR and RR at the end of Stage II will be analysed in a similar way to RR at Week 8. Estimates for the survivor function for the time-to-event variables, such as time to progression (TTP), PFS, OS, duration of response, and time to response, will be obtained by using the Kaplan-Meier (KM) approach together with associated 95% CI.

Due to the small sample size in Cohort 7 (patients with other solid tumours), only descriptive statistics will be applied. If there are at least 5 patients with the same tumour type, number (percentage) of patients will be summarized in the frequency table and listed for RR at Week 8, clinical benefit rate and BOR. If there are fewer patients, only listings will be provided. For response criteria for patients with prostate cancer, ECD and/or LCH enrolled in this cohort, see [Appendix 9](#) and [Appendix 10](#), respectively.

In case a cohort/indication is expanded up to 70 patients, the primary analysis for efficacy will occur once all patients have been followed up for 9 months after last patient had been enrolled in that cohort, or the patient develops progressive disease, withdraws consent, or is lost to follow-up, whichever occurs first.

For all patients in Cohort 1, the CT scans during the patient's last therapy prior to this study, as well as CT scans made during this study, will be collected and reviewed retrospectively by an IRC. Scans from the prior therapy will be used to establish pITT, and this may be examined in relation to the TTP achieved from study treatment. During the study, the investigator-assessed response rate will remain as the primary efficacy endpoint and the IRC assessment will be a supportive secondary endpoint. The concordance tables between Investigator and IRC assessment will be produced. The IRC assessment of response rates will focus on Week 8, Week 16 and BOR. For other cohorts, collection of scans are described in the study assessment sections. Analyses will be performed as described above for Cohort 1.

8.3.3 Safety Data Analysis

The safety variables will be summarized for the safety population where the safety population is SP1 to SP7. All safety variables will be summarized for each cohort.

All AEs will be assessed according to the NCI CTCAE, v4.0, grading system. The analysis of AEs will focus on treatment-emergent AEs, i.e., AEs occurring on the day of or after first administration of study drug (vemurafenib). Non-treatment emergent AEs (i.e., those occurring before commencement of study medication) will only be listed.

The incidence, type, and severity of AEs will be summarized according to the primary system-organ class (SOC) and within each SOC, by MedDRA preferred term. Summary tables may be presented for time to first onset of the AE of special interest.

AEs leading to treatment interruption and discontinuation and SAEs will be analysed in a similar way to all AEs. Cause of death will also be summarized and listed.

Results from skin evaluation, head and neck evaluations, chest CT scan (e.g., number of lesions, SCC - keratoacanthoma type, etc.) will be summarized using frequencies and percentages. The number of patients prematurely discontinued from the treatment with corresponding reason for discontinuation will be summarized and listed. The discontinuation from study will be also summarized and listed.

Descriptive statistics will be presented for cumulative vemurafenib doses and duration of exposure.

Laboratory parameters, haematology, and serum biochemistry will be presented in shift tables of NCI-CTCAE grade at baseline versus worst grade during the Treatment Period. The summary of laboratory parameters presented by means, standard deviation, minimum, and maximum will be also presented.

Vital signs (blood pressure, temperature, heart rate, and respiratory rate) and ECG (heart rate, PR interval, QRS duration, QT interval and QTc interval) will be summarized over time by means of mean, median, and range (mean and maximum). The ECG findings will be also presented by frequency tables over time. The ECOG PS will be summarized by frequency tables over time and percentage of patients in different categories will be presented by bar charts at different time points. Physical examination variables collected only at baseline (e.g., height) will be summarized for baseline only while other physical examination variables will be summarized over time by visits and reported in patients' listings. Concomitant therapy will be summarized by frequency tables and percentages.

For Cohort 3b, there will be a summary of DLT safety parameters (as defined in [Section 6.3.2.2](#)) by dose levels.

For Cohort 7 (patients with other solid tumours), if there are at least 5 patients with the same tumour type, number (percentage) of patients for safety parameters will be summarized and listed. If there are less patients then only listings will be provided for this cohort.

